## **11.6. Post-Study Reporting Requirements**

Although such information may not be routinely sought or collected by the Sponsor, SAEs that occur after the subject has completed a clinical study may be reported. Such cases will be evaluated for expedited reporting.

## **11.7. Regulatory Reporting of Adverse Events**

The Sponsor, or its designee, is responsible for submitting reports of suspected, unexpected, serious adverse reactions (SUSARs) to regulatory authorities on an expedited basis, according to the International Council on Harmonisation Guidelines and to other regulatory authorities according to national and local regulations as required.

The Investigator will report all SAEs that occur at his/her site to the IRB/IEC/REB per the IRB/IEC/REB regulations.

Investigators will also be notified of SUSARs that occur at other Sponsor sites and Sponsor trials using the study product. Each site is responsible for notifying its IRB/IEC/REB of these additional SUSARs in accordance with local or central IRB/IEC/REB procedures. Copies of each report will be kept in the Investigator's files and adequate documentation will be provided to the Sponsor including documentation that the IRB/IEC/REB was notified of each safety report.

## **11.8. Pregnancy**

The risks of treatment with GC4419 during pregnancy have not been evaluated. Male subjects and female subjects of childbearing potential who engage in sexual intercourse should use a

highly effective method of contraception throughout the study and for 30 days (females) or 90 days (males) following the last dose of GC4419.

For the purpose of this document, a woman is considered of childbearing potential (WOCBP), i.e. fertile, following menarche and until becoming post-menopausal unless permanently sterile.

Permanent sterilization methods include hysterectomy, bilateral salpingectomy and bilateral oophorectomy. A postmenopausal state is defined as no menses for 12 months without an alternative medical cause.

For the purpose of this document, a man is considered fertile after puberty unless permanently sterile by bilateral orchidectomy.

A highly effective method of contraceptive is defined as any methods that can achieve a failure rate of less than 1% per year when used consistently and correctly are considered as highly effective birth control methods.

Such methods include:

- combined (estrogen and progestogen containing) hormonal contraception associated with inhibition of ovulation:
  - oral
  - intravaginal
  - transdermal
- progestogen-only hormonal contraception associated with inhibition of ovulation:
  - oral
  - injectable
  - implantable
- intrauterine device (IUD)
- intrauterine hormone-releasing system (IUS)
- bilateral tubal occlusion
- vasectomized partner
- sexual abstinence

#### **11.8.1. Time Period for Collecting Pregnancy Information**

As permitted by IRB/EC/REB policies, any pregnancy that occurs from the first dose of GC4419 up to 30 days after last dose (30-Day Follow-Up Period) should be reported using the appropriate form within 24 hours of learning of the subject's pregnancy. The subject will be followed throughout the course of the pregnancy. Generally, follow-up will be no longer than 6 to 8 weeks following the estimated delivery date. Any premature termination of the pregnancy should be reported. If a pregnancy is identified outside the 30-Day Follow-Up Period, the Investigator may report using clinical judgment.

### **11.8.2. Action to be Taken if Pregnancy Occurs in a Female Partner of a Male Subject**

The Investigator will attempt to collect pregnancy information on any female partner of a male study subject who becomes pregnant while the male partner is participating in this study. In the case of paternal exposure, the investigator should obtain permission from the subject's partner in order to collect any pregnancy information. The Investigator will record pregnancy information on the appropriate form and submit it to the Sponsor within 24 hours of learning of the partner's pregnancy. The partner will also be followed to determine the outcome of the pregnancy. Information on the status of the mother and child will be forwarded to the Sponsor. Generally, follow-up will be no longer than 6 to 8 weeks following the estimated delivery date. Any premature termination of the pregnancy will be reported. If a pregnancy is identified outside the 30-Day Follow-Up Period, the Investigator may report using clinical judgment.

## **12. STATISTICS**

### **12.1. General Considerations**

A separate Statistical Analysis Plan will provide technical details of the statistical analyses to be performed, in addition to the specifications in this protocol. In the event of discrepancies between the protocol and the Statistical Analysis Plan, the latter will control the analyses performed.

All statistical analyses will be conducted with the SAS® software package version 9.2 or higher.

#### **12.1.1. Randomization and Stratification**

Not applicable.

### **12.2. Sample Size**

The sample size is selected with the intent that it will contribute to an overall safety database of 300 subjects with head and neck cancer who will, across all studies of GC4419, have received a full course of GC4419 at the intended dose (90 mg), schedule (1-hour infusion, 5 days/week, prior to IMRT), and duration (single course of 6-7 weeks) in combination with concurrent IMRT and cisplatin. Up to 70 such subjects are expected to be needed to reach the total safety database of 300. Enrolling up to 70 patients to the present study is expected to provide these subjects, assuming that approximately 10-20% will discontinue GC4419 before receiving it for at least 6 weeks.

The overall safety database size of 300 will allow for detection with 95% probability of adverse events of 1% true incidence in at least 1 subject.

Enrollment may be adjusted to ensure an overall safety database size of 300 across the development program.

### **12.3. Analysis Populations**

Safety and efficacy analyses will be conducted on an "intent to treat" (ITT) population, consisting of all enrolled subjects who receive at least one dose of GC4419, and on a "per protocol" population consisting of subjects who receive at least 60 Gy of IMRT and at least 5 weeks (25 doses) of GC4419.

Subjects who withdraw prior to any dosing will have their reasons for withdrawal noted.

### **12.4. Safety Analysis**

AEs will be grouped by system organ class, high level term, and preferred term according to the Medical Dictionary for Regulatory Activities (MedDRA) dictionary. Incidence by subject will be tabulated for all treatment-emergent, serious, severe, and treatment-related adverse events. Detailed listings will be provided for all serious adverse events, deaths, and withdrawals due to adverse events.

Laboratory measurements and vital signs will be summarized by treatment group at each of the protocol-specified time points.

Safety parameters will be summarized with descriptive statistics on the safety population, defined as the ITT population; viz., all subjects who received at least one dose of GC4419.

Further details will be provided in the study's Statistical Analysis Plan.

## **12.5. Efficacy Analysis**

Overall rates of SOM/Grade 4 OM incidence and number of SOM/Grade 4 days will be summarized descriptively.

### **12.5.1. Multiplicity**

Not applicable.

### **12.5.2. Handling of Missing Data**

Subjects who withdraw consent for GC4419 administration should be encouraged to continue and complete standard IMRT/cisplatin, and protocol assessments.

The study's Statistical Analysis Plan will discuss the handling of missing data for subjects who lack WHO OM scores, who discontinue from the study without complete OM follow-up of WHO OM scores, and whose resolution date of severe OM is unknown.

### **12.5.3. Covariate Adjustment**

Not applicable.

## **12.6. Exploratory Analyses**

Any exploratory analyses will be described in the Statistical Analysis Plan.

## **12.7. ETHICS**

### **12.7.1. Ethical Conduct of the Study**

The Investigator will ensure that this study is conducted in full compliance with the principles of the "Declaration of Helsinki" (version October 2008), ICH guidelines, in particular ICH-GCP, or with the laws and regulations of the country in which the research is conducted, whichever affords the greatest protection to the study subject. The Investigator will also assure that the basic principles outlined in "ICH Guideline for Good Clinical Practice" as published in the Federal Register May 9, 1997, and all applicable Federal regulations are adhered to.

### **12.7.2. Institutional Review Board (IRB)/Independent Ethics Committee (IEC)/Research Ethics Board (REB) Approval**

This protocol and any accompanying material to be provided to the subject (such as advertisements, information sheets, or descriptions of the study used to obtain informed consent) will be submitted, by the Investigator, to an IRB/IEC/REB. Approval from the IRB/IEC/REB must be obtained, and a copy must be provided to the Sponsor or its representatives before initiating the conduct of any study procedures including screening or enrolling any patients into the study.

No modifications or deviations from this protocol other than those that are deemed medically necessary by the Principal Investigator or designated sub-Investigator are to be made without prior, written approval by the Sponsor. Significant protocol deviations will be reported to the Sponsor and to the IRB/IEC/REB in accordance with its reporting policy.

Any modifications made to the protocol by the Sponsor after receipt of IRB/IEC/REB approval must be submitted to the committee for approval prior to implementation.

## **12.8. Written Informed Consent**

In accordance with regulatory and local IRB/IEC/REB requirements, before study procedures are performed, patients will be informed about the study and required to sign the IRB/IEC/REB approved Informed Consent Form (ICF). This form will be signed after adequate explanation of the aims, methods, objective and potential hazards of the study and prior to undertaking any study-related procedures. The Sponsor or its designee will provide an ICF template to the Investigator. The Sponsor or its designee must approve changes to the ICF template prior to submission to the IRB/IEC/REB. Informed consent will be obtained according to the applicable IRB/IEC/REB requirements. No patient is to be screened or treated until an ICF, written in a language in which the patient is fluent, has been obtained. The signed ICF will be retained with the study records. Each patient will also be given a copy of his/her signed ICF.

## **12.9. Data Monitoring Committee (DMC)**

Not applicable.

## **13. DIRECT ACCESS TO SOURCE DATA/DOCUMENTS**

### **13.1. Study Monitoring**

In accordance with ICH-GCP guidelines, the study monitor must have direct access to the Investigator's source documentation in order to verify the consistency of the data recorded in the electronic CRFs.

The monitor is responsible for routine review of the electronic CRFs at regular intervals throughout the study, to verify adherence to the protocol, and the completeness, consistency and accuracy of the data being entered on them. The monitor should have full access to any subject records needed to verify the entries on the electronic CRFs. The Investigator agrees to cooperate with the monitor to assure that any follow-up items identified in the course of these monitoring visits are resolved.

During site visits, the monitor will:

- Check the progress of the study;
- Review study data collected;
- Conduct source document verification;
- Identify any issues and address their resolution.

This will be done in order to verify that the:

- Data are authentic, accurate, and complete;
- Safety and rights of subjects are being protected;
- Study is conducted in accordance with the currently approved protocol (and any amendments), GCP, and all applicable regulatory requirements.

The Investigator agrees to allow the monitor direct access to all relevant documents and to allocate his/her time and the time of his/her staff to the monitor to discuss findings and any relevant issues.

### **13.2. Audits and Inspections**

Authorized representatives of the Sponsor, a regulatory authority, an Independent Ethics Committee or an Institutional Review Board may visit the site to perform audits or inspections, including source data verification. The purpose of a Sponsor audit or inspection is to systematically and independently examine all study-related activities and documents to determine whether these activities were conducted, and data were recorded, analyzed, and accurately reported according to the protocol, GCP guidelines of the ICH, and any applicable regulatory requirements. The Investigator should contact the Sponsor immediately if contacted by a regulatory agency about an inspection.

### **13.3. Protocol Compliance**

The Investigator is responsible for ensuring the study is conducted in accordance with the procedures and evaluations described in this protocol.

## **13.4. Protocol Modifications**

Protocol modifications, except those intended to reduce immediate risk to study subjects, may be made only by the Sponsor or its representatives. All protocol modifications must be submitted to the IRB/IEC/REB in accordance with local requirements. Approval must be obtained before changes can be implemented.

## **13.5. Information Disclosure**

### **13.5.1. Ownership**

All information provided by the Sponsor or its representatives, and all data and information generated by the site as part of the study (other than a subject's medical records), are the sole property of the Sponsor.

### **13.5.2. Confidentiality**

All information provided by the Sponsor or its representatives, and all data and information generated by the site as part of the study (other than a subject's medical records) will be kept confidential by the Investigator and other site staff. Information related to this study is subject to the confidentiality provisions of the Clinical Research Agreement between the investigative site and the Sponsor.

### **13.5.3. Publication**

All publication or presentation rights for the findings of the clinical investigation under this protocol shall be governed by the appropriate terms of the Clinical Research Agreement between the investigational site and the Sponsor.

## **14. QUALITY CONTROL AND QUALITY ASSURANCE**

The study will be monitored and managed in accordance with ICH-GCP.

To ensure compliance with GCP and all applicable regulatory requirements, the Sponsor or its representatives may conduct a quality assurance audit. Regulatory agencies may also conduct a regulatory inspection of this study. Such audits/inspections can occur at any time during or after completion of the study. If an audit or inspection occurs, the Investigator and institution agree to allow the auditor/inspector direct access to all relevant documents and to allocate his/her time and the time of his/her staff to the auditor/inspector to discuss findings and any relevant issues.

## **15. DATA HANDLING AND RECORDKEEPING**

### **15.1. Case Report Forms**

All required study data must be recorded on the electronic CRF provided by the Sponsor or its representatives. The data recorded onto the electronic CRF is derived from the source documents. The Investigator shall ensure that all data in the electronic CRF is accurate and consistent with the source documents or that any discrepancies of the electronic CRF with source documents are explained (ICH-GCP 4.9.2).

Electronic case report forms will be accessed by the study center for collection of all study data, and a copy of the electronic CRF will be provided to the site for the Investigator files. For each subject, the electronic CRF must be completed by site staff and must be signed electronically by the Principal Investigator in a timely fashion after data collection. If a subject withdraws from the study, the electronic CRFs should be promptly completed and the reason for withdrawal must be noted. If a subject is withdrawn from the study because of a drug-related toxicity, thorough efforts should be made to clearly document the outcome.

### **15.2. Retention/Inspection of Records**

The Investigator must maintain adequate and accurate records to enable the conduct of the study to be fully documented and the study data to be subsequently verified.

Records of drug receipt and disposition, electronic file of CRFs, source documents, reports of this investigation and other study documentation must be maintained by the Investigator for a period of at least 25 years following the date on which the investigational drug is approved by FDA or other applicable regulatory agency for marketing for the purposes that were the subject of the clinical investigations. If no application is to be filed, records must be retained until 25 years following the date that the study is discontinued, and the FDA or other applicable regulatory agency is notified. If the application is not approved by the FDA or other applicable regulatory agency for such indication, records must be retained for 25 years after notification by the Sponsor of the FDA or other applicable regulatory agency decision. The records must be available for copying and inspection if requested by regulatory authorities.

The Sponsor should be notified in writing at least 30 days prior to the disposal or transfer to another location or party of any study records related to this protocol.

## APPENDIX 1. SCHEDULE OF ASSESSMENTS

**Table 5: Schedule of Assessments**

Assessments	Screening	Treatment Period								OM Follow-Up
		≤28 days of IMRT Day 1		Wk 1	Wk 2	Wk 3	Wk 4	Wk 5	Wk 6	
		Day 1	Days 2-7	Days 8-14	Days 15-21	Days 22-28	Days 29-35	Days 36-42	Days 43-49	Last Day of IMRT or Early Term 
Informed consent	X									
Inclusion/exclusion criteria 	X	X								
Dental exam/IMRT clearance	X									
Medical and HNC histories 	X									
Complete physical exam 	X									X
Height	X									
Weight	X	X		X	X	X	X	X	X	
Vital signs, ECOG 	X	X			X			X	X	
Record BSA 		X		X	X	X	X	X		
Tumor imaging 	X									
Concomitant medications 		X	Weekdays							X
Adverse Events 		X	Weekdays							X
ECG (12-lead) 	X									
OM assessment 	X	X	Twice-weekly							X
Symptom Related Questionnaire 	X	X	X	X	X	X	X	X		X
Blood draw: Serum pregnancy 	X									X
Blood draw: Lab safety tests 	X	X	X	X	X	X	X	X		X 
Blood draw: PK 		X	X		X					
Urine Pregnancy Test 		X			X					
Dosing GC4419 		X	Weekdays when IMRT is given							X

BSA = body surface area; ECG = electrocardiogram; ECOG = Eastern Cooperative Oncology Group; HNC = head and neck cancer, IMRT = intensity-modulated radiation therapy; OM = oral mucositis; PE = physical examination; PK = pharmacokinetics

### Table footnotes

 If a subject ends study participation early and/or withdraws consent after Baseline (Day 1), all last day of IMRT procedures should be completed.

 The Post-IMRT OM and Safety Follow-up Visits will be scheduled based on the last day of IMRT. All subjects will be seen at Days 7, 14, 21 and 28 ( $\pm 2$  calendar days) from the last day of IMRT.

 See protocol Sections 7.1 and 7.2.

 The HNC history should include tumor HPV status, staging (AJCC 8th Edition) information, prior treatments, and confirmation of histopathological diagnosis of SCC. Medical conditions and illnesses that have occurred since the subject signed the ICF up until the date of enrollment should be recorded as medical history. Medical history also includes tobacco and alcohol use history.

 At the Screening and Last Day of IMRT Visits, a complete physical examination will be conducted.

 Vital signs (temperature, systolic and diastolic blood pressures, heart rate, and respiration rate), and ECOG will be obtained and recorded at the Screening and Baseline Visits, once during Weeks 4 and 7, and at the Last Day of IMRT Visit. All vital signs should be measured following 2 minutes of rest in the sitting position. On Day 1 (Baseline) and Day 22, blood pressure must be measured at the following times: 1) within 30 minutes prior to the pre-GC4419 PK draw, and 2) after GC4419 infusion, prior to standing and prior to the End of GC4419 Infusion PK draw.

 For subjects receiving tri-weekly cisplatin, body surface area (BSA) will be recorded to confirm cisplatin dosing at the Baseline Visit and once during Weeks 4 and 7. For subjects receiving weekly cisplatin, BSA will be recorded to confirm cisplatin dosing at the Baseline Visit and once per week until chemotherapy is completed.

 Radiographic imaging must be performed within 60 days prior to the first day of IMRT for all subjects.

 All concomitant therapies (e.g., prescription and over-the-counter medications) taken by subjects on or after the date of enrollment through 30 days following the last dose of GC4419, IMRT or cisplatin (i.e. whichever occurs last) will be collected in the CRF. Any concomitant therapies used to treat any serious or related adverse event will be recorded in the CRF.

AEs and SAEs with onset dates on or after the date of enrollment through 30 days following the last dose of GC4419, IMRT or cisplatin (i.e. whichever occurs last) will be recorded on the CRF. All subjects with SAEs will be followed until the events resolve, stabilize, become chronic, the subject completes the study, or the subject is lost to follow-up.

 Ventricular rate and P-R, QRS, QT, and QTc intervals will be assessed and recorded at Screening.

All OM assessments must be performed by trained evaluators. The extent of the subject's OM will be scored using the WHO OM toxicity scale. OM assessments will be completed at the Screening Visit, at the Baseline Visit, twice weekly (no less than two days apart) within each 5-day IMRT period and on the last day of IMRT or Early Termination Visit. For Week 1, the first OM assessment will occur at the Baseline Visit and one additional OM assessment must occur at least two days later during the week. The extent of the subject's OM will be scored using the WHO OM toxicity scale. OM assessments should continue weekly for four weeks following the last day of IMRT (Day 7, Day 14, Day 21 and Day 28  $\pm 2$  calendar days).

Symptom Related Questionnaires to be completed by subjects prior to the OM assessment at W1D1, and then prior to the second OM assessment each week and 28 days ( $\pm 2$  calendar days) post end of treatment (EOT).

For a woman of childbearing potential, serum pregnancy test must be performed at the Screening Visit and at the Last Day of IMRT or Early Termination Visit.

Clinical laboratory measurements will be conducted at the Screening Visit, twice during Week 1 (once at the Baseline Visit and again on Day 3, 4 or 5), and once weekly from Week 2 through the last day of IMRT. Clinical laboratory measurements at these visits will include the hematology profile (hemoglobin, hematocrit, red blood cell count, white blood cell count with differential, and platelet count. Differential to include total neutrophils, lymphocytes, monocytes, eosinophils, and basophils) and chemistry profile (glucose, BUN, creatinine, sodium, potassium, calcium, albumin, total protein, total bilirubin, direct bilirubin, alkaline phosphatase, ALT (SGPT), AST (SGOT), chloride, phosphate, bicarbonate, magnesium).

If safety labs have already been drawn during the study week in which the last day of IMRT or early termination visit falls, then lab safety tests (chemistry and hematology profiles) do not need to be conducted on the last day of IMRT or at the early termination visit. If safety labs have not been drawn during the current study week at the time of the early termination visit or on the last day of IMRT, then safety labs should be drawn on that day. Safety labs only need to be drawn once per study week after Week 1.

Blood samples will be collected for GC4419 pharmacokinetic (PK) measurements at Baseline (Day 1), Day 2, and Day 22. See Section 10.5 for details.

 For women of childbearing potential, urine pregnancy tests should be administered at Baseline (Day 1) and Q4 weeks from enrollment.

GC4419 will be administered up to 35 times: weekly, Monday through Friday, beginning at Baseline (IMRT Day 1) and continuing through the 35th dose.

IMRT must begin no longer than four hours following the end of the GC4419 infusion. If IMRT is not received on any given day due to a treatment break or unforeseen circumstances, GC4419 should not be administered on that day. Subjects should resume GC4419 administration when IMRT resumes. If GC4419 was already administered on a given day and IMRT is not administered due to unforeseen circumstances, that day's GC4419 dose will still count as one of the 35 doses.

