16. Medical history that includes any condition, or requires the use of concomitant medications which, in the Investigator's judgment, are associated with or create a risk of increased carotid sinus sensitivity, symptomatic bradycardia, or syncopal episodes.

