In vitro, GC4419 inhibited cytochrome P450 isozyme 2D6 (CYP2D6) with an IC50 of 0.079  $\mu$ M. Concurrent administration of GC4419 with CYP2D6 substrates should be done with caution, and the need for a decreased dose of the CYP2D6 substrate should be considered, especially for substrates with a narrow therapeutic range. CYP2D6 substrates include certain beta blockers (e.g., propranolol and metoprolol), antidepressants (e.g., tricyclics), antipsychotics (e.g., phenothiazines and most atypicals), and antiarrhythmics (e.g., propafenone, flecainide).

Mouthwashes or rinses containing sodium bicarbonate, clotrimazole (Mycelex), nystatin, fluconazole (Diflucan), viscous xylocaine, and/or viscous lidocaine are permitted. If a subject uses “Magic Mouthwashes” or “Miracle Mouthwashes,” all ingredients must be recorded in the subject’s medical record in order to confirm the mouthwashes did not contain the prohibited ingredients listed above.

All medication restrictions end after post-IMRT OM follow-up is completed unless otherwise noted.

Subjects who receive prohibited medications will not automatically be removed from the study; however, administration of a prohibited medication is a significant deviation from the protocol and must be reported to the Medical Monitor as soon as possible and the presiding IRB/IEC/REB (per institutional guidelines). The decision for study continuation or discontinuation will be made at that time on a case-by-case basis and in consideration of the clinical requirement and circumstances.

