### **10.1. Safety Assessments**

Safety will be assessed on the basis of treatment-emergent AEs, physical examination findings, clinical laboratory tests, electrocardiogram (ECG) measurements, and vital sign measurements.

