### 10.7.1. Screening

Screening assessments and procedures will be completed within 28 days of IMRT and GC4419 start.

- Obtain a signed IRB/IEC/REB-approved informed consent form (ICF)
- Confirm subject eligibility by reviewing inclusion/exclusion criteria
- Ensure a dental examination was conducted for IMRT clearance and potential sources of mucosal irritation (e.g., tooth extraction) were eliminated. The dental exam must occur

within the 28-day screening period. The exam must be performed by a licensed clinician, but not necessarily by a dentist. For edentulous subjects, the subject must be cleared for IMRT per SOC (i.e., oral exam).

- Obtain medical history, tobacco use history, and alcohol use history
- Obtain HNC history; HNC history should include:
  - Tumor HPV status, for oropharyngeal cancers
  - Pre-treatment tumor imaging (See Section 10.6.2.1); may be completed within 60 days prior to the first day of IMRT)
  - Prior treatments
  - Confirmation of histopathological diagnosis of SCC
  - Tumor staging (AJCC 8th Edition) (pre-surgical staging for surgical subjects if available; otherwise, provide post-surgical staging)
- Conduct a complete physical examination, including height
- Measure vital signs, body weight, and ECOG Performance Status
- Confirm required Radiographic imaging performed within 60 days prior to first day of IMRT per [Section 10.6.1.1](#).
- Conduct a 12-lead ECG.
- Conduct OM assessment per [Appendix 2](#) and record the WHO score
- Draw blood for clinical laboratory measurements per [Section 10.1.2](#) to include hematology profile, serum chemistry profile and serum pregnancy test for women of childbearing potential
- Record planned IMRT and chemotherapy parameters
- Record/update medical conditions and illnesses that have occurred since the subject signed the ICF and record in medical history
- All questions related to subject eligibility should be directed to Galera's Medical Monitor or designee.

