### **11.2.3. Clinical Laboratory Abnormalities and Other Abnormal Assessments as AEs and SAEs**

Clinically significant abnormal laboratory findings or other abnormal assessments that are associated with the disease being studied, unless judged by the Investigator as more severe than expected for the subject's condition, or that are present or detected at the time of enrollment and prior to study drug dosing that do not worsen, will not be reported as AEs or SAEs.

Laboratory abnormalities should only be recorded in the Adverse Event section of the CRF if at least one of the following criteria is met:

- Meets the criteria of an SAE
- Resulted in a dose reduction and/or delay in the administration of GC4419, IMRT, and/or cisplatin
- Treatment is initiated for the abnormality
- Investigational product was discontinued
- Grade 3 or Grade 4 per NCI CTCAE v5.0

All other abnormal laboratory findings will be captured via laboratory CRF pages and noted in shift tables.

Abnormal assessments (e.g., ECGs) that are judged by the Investigator as clinically significant will be recorded as AEs or SAEs if they meet the definitions as defined in [Section 11.1](#).

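### Section 10.1 bases safety partly on ECG, but the only scheduled ECG precedes treatment, and no heart rate is explicitly required after the same day's infusion

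*Combined protocol and SAP*

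**What the plan says.** Section 10.1 sets out the basis of the safety assessment: "Safety will be assessed on the basis of treatment-emergent AEs, physical examination findings, clinical laboratory tests, electrocardiogram (ECG) measurements, and vital sign measurements". Section 10.1.1 then lists the ECG parameters to be measured.

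The schedule has one ECG. Section 10.7.1 (Screening) has the instruction "Conduct a 12-lead ECG", and Table 5, footnote 11 agrees: "Ventricular rate and P-R, QRS, QT, and QTc intervals will be assessed and recorded at Screening". Screening falls within the 28 days before IMRT and GC4419 start. Sections 10.7.2 (treatment) and 10.7.3 (follow-up) list no ECG. Section 11.2.3 says what happens to an abnormal tracing: "Abnormal assessments (e.g., ECGs) that are judged by the Investigator as clinically significant will be recorded as AEs or SAEs", provided that the definitions in 11.1 are met.

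Heart rate is one of the vital signs (10.1.1; Table 5, footnote 6). These are due at Screening, on Day 1, once in Week 4, once in Week 7 and any additional IMRT weeks, and on the Last Day of IMRT. Blood pressure has an extra rule: on Days 1 and 22 it is taken before the pre-dose PK draw and again after the infusion, before the subject stands. Section 10.7.2.3 repeats the post-infusion blood pressure and names no other vital sign.

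Exclusion 16 in Section 7.2 covers conditions and medications that "create a risk of increased carotid sinus sensitivity, symptomatic bradycardia, or syncopal episodes". Section 8.9.1 prohibits medications on the same three grounds.

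**The concern.** Safety is the primary objective. A protocol that names ECG as a basis of safety leads the reader of the study report to expect on-treatment ECG data. Under this schedule a report would contain few or no ECG abnormalities, and nothing in the plan tells the reader that none were systematically looked for. The data also feed a pooled safety database of 300 subjects (Section 12.2), where the absence could be carried forward as reassurance.

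The heart-rate gap matters for a related reason. The protocol expects haemodynamic effects around the infusion: Section 9.1 acts on hypotension within 2 hours of its start. It also treats symptomatic bradycardia and syncope as risks serious enough to exclude subjects and prohibit drugs. Yet the one reading tied to the end of an infusion is blood pressure alone.

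**Working it through.** No sample size, power or error rate is involved, and the plan states no figure on this point to reproduce. The check is a count of scheduled time points from Sections 10.1.1 and 10.7.1 to 10.7.3 and Table 5 with footnotes 6 and 11.

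| Measurement | Screening and Day 1 | Later days, after earlier infusions | Explicitly required after the same day's infusion |
|---|---|---|---|
| 12-lead ECG | 1 (Screening) | 0 | 0 |
| Heart rate | 2 (Screening, Day 1) | 3 (Week 4, Week 7, Last Day of IMRT) | 0 |
| Blood pressure | Screening, Day 1 | Week 4, Week 7, Last Day of IMRT | 2 (Day 1, Day 22) |

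**ECG.** Section 11.2.2 treats a condition with onset before the first dose as medical history. Table 5, footnote 10 instead collects AEs from enrolment. The result is the same under either rule, because Section 10 requires screening evaluations to be complete before enrolment. The one scheduled ECG therefore cannot itself produce a treatment-emergent finding, and no later scheduled ECG exists from which to compute a change. Section 12.4 plans summaries of AEs, laboratory values and vital signs and does not mention ECG, so the protocol's analysis text does not resolve the mismatch.

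**Heart rate over the course.** Scheduled occasions: 1 + 1 + 3 = 5 in a seven-week course, more if IMRT runs longer. In Table 2's example, Week 4 begins after 3 × 5 = 15 infusions and Week 7 after 6 × 5 = 30. A course of 60 Gy at 2.0 Gy is 60 / 2.0 = 30 fractions, or six weeks at five per week; without a Week 7, two later occasions remain. A low value at any of these, set against Screening or Day 1, would count as treatment-emergent.

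**Heart rate around an infusion.** Vital signs appear under the pre-infusion heading of 10.7.2.1. That section is loosely built: it also contains Last Day of IMRT procedures and the post-infusion blood pressure. Section 10.1.1 and footnote 6 give no time for heart rate relative to the infusion. A site may take it before or after; no text requires it after. Required same-day post-infusion heart rates: 0, against 2 blood pressures.

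**The case against.** The strongest reply is that the ECG issue is one of wording. The primary endpoints in Section 5.2 are AEs, SAEs and laboratory abnormalities; ECG is not among them, and no ECG table is promised. Section 11.2.3 can operate on an unscheduled tracing, for which the Screening ECG is the comparator. The Screening ECG may also help an investigator apply exclusion 16. Whether on-treatment ECGs are needed depends on earlier data in the Investigator's Brochure, which is not available here, and with no control arm and concurrent cisplatin a change from Screening would be hard to attribute. All of this stands. It is why added ECGs are not part of the fix, but it does not remove the mismatch between 10.1 and the schedule.

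Two stronger readings are tempting, and the documents do not support them:

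- A reader might infer that no bradycardia finding can come from the schedule. Heart rate is measured on treatment, and Table 5 has AEs recorded on weekdays, so symptomatic bradycardia or syncope has a reporting route. What is missing is a required reading after the same day's infusion.
- A reader might infer from the CYP2D6 caution in 8.9.1 that beta blockers and antiarrhythmics are simply allowed. The same section prohibits drugs that the investigator judges could create a risk of symptomatic bradycardia or syncope, and exclusion 16 covers such medication at entry. The caution describes a metabolic interaction; it is not a stated ECG signal for GC4419.

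**Conclusion.** The point holds in two limited parts. First, Section 10.1 names ECG as a basis of safety, while the schedule provides one ECG before treatment and none on or after the first dose, for any of up to 70 subjects. The schedule cannot yield a treatment-emergent ECG change. Second, no heart rate is explicitly required after that day's infusion on any dosing day, so an acute infusion-related fall in heart rate is not systematically captured, although the protocol names the risk.

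This rests on the protocol text. Section 12.1 refers to a separate Statistical Analysis Plan, which could add analyses but could not create measurements that were never scheduled. It also assumes that the timing of vital signs is not fixed in a site manual outside these documents. The size of any cardiac effect is unknown, and nothing here suggests that one exists. The weakness is in what the study could show.

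**What to change.** 1. In 10.1.1, 10.7.2.1, 10.7.2.3 and Table 5, footnote 6, require heart rate to be recorded with each pre- and post-infusion blood pressure on Days 1 and 22. Add to 12.4 a descriptive summary of the within-day change (post minus pre) on each day. The cost is one more recorded value per reading: 2 days × 2 readings = 4 per subject, at most 4 × 70 = 280 in the study. Some of the pre-infusion values may already be collected as vital signs.

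2. Reconcile 10.1 with the ECG schedule. Describe the ECG as a Screening assessment and remove it as a basis for treatment-emergent safety. State in the report that no on-treatment ECG was scheduled, so that an absence of ECG findings is not read as evidence of cardiac safety. This is wording only.

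On-treatment ECGs remain an option for the sponsor. They add a procedure, their timing is debatable, and neither change above depends on them.
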